Step 3: open PALstudio app, make sure the docking station is plugged into the USB port, and place the monitor in the end spot that says “PC interface”.

Step 4: click on “transfer”, the computer then looks to find the ActivPal. It will show you the serial number of the ActiPal data that is getting downloaded. Double check to make sure the one you mean to be downloading is in fact the one getting downloaded. This takes a few minutes so work on something else while you wait. Once the files are then downloaded and then “verified” by the program.

Step 5: Open BOX Health, verify the file is there and open file to be sure data is in the file.

Step 6: Click on Analyze in the PAL studio app, click on all 4 boxes to get all data.

Step 7: Click on Reports and chose the “ASOD”- The standard algorithm with inverted wear correction” option then click Generate reports.

Step 8: Look in BOX Health and verify the file is there and open all files to be sure there is data in the file.

Instructions for Participants

BISTRO Patient: ActivPAL Instructions

Table of Contents

| | |
|-----------------------------|---|
| Information about the study | 2 |
| How to Apply the ActivPAL | 3 |
| How to Remove the ActivPAL | 5 |

The ActivPAL is designed to monitor activity levels and identify periods of sitting/lying, standing, and walking. We have incorporated the ActivPAL into our study to determine if the intervention will affect your activity level and exercising habits. We ask that you wear it 3 times during the study for one week each time. First when you begin the study, second after participating in the intervention, and third at the 3-month mark following completion of cardiac rehabilitation.

During each use, we request that you wear the ActivPAL on your thigh, 24 hours a day for 7 days. We will supply a waterproof covering for the ActivPAL, which will cover the ActivPAL at all times, even when you shower. If needed, extra materials to reapply the ActivPAL will be supplied at no cost to you.

Once the ActivPal is programed for your use, the bottom light on the ActivPAL will flash green. If the light stops flashing at any time during the week you have it, please contact the research assistant listed in the study paperwork given to you when you joined the study. Also, if skin irritation occurs at any time while you are wearing it, please contact the research assistant.

How to Apply the ActivPAL:

1. Carefully wash and dry the area of skin where the ActivPAL will applied.
2. Obtain the ActivPAL. Orient it so that the body on the ActivPAL is standing up. (See picture above.) You will notice the rounded side is up, and the square side is down. Lights face away from your skin.
3. Cover the ActivPAL with the waterproof covering and roll the end to the side away from you.
4. Sit down on a chair when attaching the monitor so that it will be easier to find the best place for attachment. You want to place it on the top 1/3rd of the length between your groin and your knee in the midline width of your thigh as shown in the picture below.

5. Apply the Skin-PREP wipe to the area of skin where the ActivPAL will be. This will protect your skin from the adhesives in the tape and allow the tape to perform better.
6. Place the covered ActivPAL in the correct orientation on the upper thigh. See picture above. The ActivPAL should be worn on your non-dominant side.
7. Use a large piece of Tegaderm tape to completely cover the ActivPAL. Ensure that this adheres directly to the skin.

Removing the ActivPAL:

1. Carefully peel the Tegaderm away from the skin by lifting up a single corner of the material and gently pulling away from your skin, but level to the bandage.
2. Remove the ActivPAL, encased in its waterproof covering, from the skin.
3. Carefully wash and dry the skin where the ActivPAL was applied with mild soap. If skin irritation has occurred, please contact research assistant.
4. Place the ActivPAL in the bubble mailer we gave to you and place it in any US mail box for return to us.
5. ActivPAL needs to be received by us before we can issue your study participation check.

If you have any questions about the ActivPAL or the study at any time please call the research assistant.

Thank you for participating in our study!

Section 12B SOP for EMPI

EMPI Standard Operating Procedure for setting up TENS

Machine Set up: do this before you see the participant. Please note, you may not need to make adjustments to the machine due to previous programming, so if the correct option is chosen move on to the next item.

1. Turn on machine
2. Press “Home” button
3. Press the TENS button (bottom Left)
4. Press the lower left bottom button until “Custom”, then press OK
5. Change “Time” to 15 MIN, Use the right buttons to raise or lower to 15 MIN, then press bottom left button to progress to “Rate”.
6. Leave “Rate” at 100Hz , then press the bottom left button to progress “Cycle”
7. Set “Cycle” to 15S, then press the bottom left button to progress to “Span”
8. Set “Span” to 50%, then press the bottom left button to progress to “Mode”
9. Set “Mode” at MOD, then Press OK
10. Now the machine is set up for participant to test the comfort level.

Once the Data collector has told you the participant is ready for the intervention explain the machine to them by giving them the EMPI handout and going through each step with the participant following the directions and you clarifying when necessary. Make sure a garbage can and table with a bowl for warm water and wash cloth and towel is within reach, (show them how to use the trimmer if necessary), give them the EMPI handout, go through each step of the process with them. Once the patches are placed and the participant is ready to turn on the machine, show them the picture on page 3 and explain the need to use the on/off button and the increase/decrease intensity buttons. Have them start increasing the intensity on either channel slowly at first and closely monitor their reactions to it. For this intervention we are just looking for a general “feeling it”. They should not increase the intensity to the point where a muscle contraction happens!

Once you are confident the participant settings are comfortable for the patient and only intensity needs to be adjusted, LOCK the device so the participant cannot change the settings themselves.

1. Press the Home button, config (right lower), locks (right lower)
2. Notice the NMES L. Muscles and press the right top button, which locks that option
3. Press the left lower button to bring up S. Muscles and press the right top button twice to get a circle with a line through it. Now that option will no longer show for participants. Repeat for TENS and Edema then press home and note only L. Muscles is an option besides config.

EMPI Standard Operating Procedure for setting up NMES

Machine Set up: do this before you see the participant. Please note, you may not need to make adjustments to the machine due to previous programming, so if the correct option is chosen move on to the next item.

1. Turn on machine
2. Press “Home” button
3. Press the NMES button (top left)
4. Large muscle (top left)
5. Press the Custom button (bottom right)
6. Change time to 15 minutes, then press bottom left button to progress to “off time”
7. Change Off time to 15 Seconds, then press bottom left button to progress to “rate”
8. Increase “Rate” to 50Hz, then press the bottom left button to progress to “Width”
9. Leave “Width” at 300 to start. Press bottom left button to progress “waveform”.
10. Leave “waveform” at SYM/ASY
11. Change Cycling “LAG” for both legs at the same time.
12. Leave “Lag” at 0S
13. Leave “CH1 Ramp +” at 2S
14. Increase “ON TIME 1” to 11S
15. Leave “CH1 RAMP –” at 2S
16. Leave “CH2 Ramp +” at 2S
17. Increase “ON TIME 2” to 11S
18. Leave “CH1 RAMP –” at 2S, then press OK
19. Now the machine is set up for participant to test the comfort level.

Once the Data collector has told you the participant is ready for the intervention explain the machine to them by giving them the EMPI handout and going through each step with the participant following the directions and you clarifying when necessary. Make sure a garbage can and table with a bowl for warm water and wash cloth and towel is within reach, (show them how to use the trimmer if necessary), give them the EMPI handout, go through each step of the process with them. Once the patches are placed and the participant is ready to turn on the machine, show them the picture on page 3 and explain the need to use the on/off button and the increase/decrease intensity buttons. Have them start increasing the intensity on either channel slowly at first and closely monitor their reactions to it. The intensity needs to be strong enough to cause the muscle to contract. Demonstrate how actively using the muscle during the contraction lessens any discomfort.

20. If the participant reports the feeling is uncomfortable or “biting” adjust the “Rate” to make the sensation more “smooth”. Decrease the Rate by 5 to 45 then have the participant try again. (Can adjust in increments of ±1 to get the “best” feel for participants. Be sure to record the final setting you programmed into the machine in both Redcap and the participant call sheet.) To make adjustments to Rate, (you not the

participant!) press the home button, NMES, Custom, the press the left lower button until you see “Rate”, then use the right lower button to make the adjustment, then press OK and have the participant try again.

21. If the participant reports the feeling is still uncomfortable or “bit” lower the WIDTH by 8 and see if that makes it better. (Can adjust in increments of ±4 to get the “best” feel for participants. Be sure to record the final setting you programmed into the machine in Redcap and on your participant call sheet.) To make adjustments to Width, You (not the participant!) need to press the home button, NMES, Custom, the press the left lower button until you see “Width”, then use the right lower button to make the adjustment, then press OK and have the participant try again.

Once you are confident the participant settings are comfortable for the patient and only intensity needs to be adjusted, LOCK the device so the participant cannot change the settings themselves.

1. Press the Home button, config (right lower), locks (right lower)
2. Notice the NMES L. Muscles and press the right top button, which locks that option
3. Press the left lower button to bring up S. Muscles and press the right top button twice to get a circle with a line through it. Now that option will no longer show for participants. Repeat for TENS and Edema then press home and note only L. Muscles is an option besides config.

Standard operating procedure when EMPI units are returned

Expect participants to bring the unit in the study canvas bag along with any unused sealed supplies.

Step 1: log into RedCap, bring up the data entry for the EMPI machine, enter the study ID.

Step 2: once you have the Canvas bag with EMPI unit, use the wipes designated for cleaning the machine to wipe down the outside of the machine and the lead wires and allow them to air dry.

Step 3: turn on the machine, identify if NMES or TENS showing on the main menu and enter that data into RedCap

Step 4: press the home button, config button (right lower), data button (left upper).

Step 5: enter the number of sessions into RedCap, press the left down button

Step 6: enter the Total hours into RedCap, press the left down button

Step 7: enter the average time into RedCap, press the left down button

Step 8: enter the CH 1 intensity into RedCap, press the left down button

Step 9: enter the CH 2 intensity into RedCap, press the home button. Double check you have entered all data into RedCap.

Step 10: press the home button, config, clear (right lower), data, and then home. The data has been erased from the machine and is ready for the next participants set up.

BISTRO Patient Instructions:

Empi Unit

| Table of Contents | Page number |
|-----------------------------------|--------------------|
| Skin Preparation | 2 |
| Using Your Empi Unit | 3 |
| Caring for the Empi Unit | 6 |
| Troubleshooting for the Empi Unit | 6 |

We have provided the following with your Empi unit for your use during the study: a canvas bag, patches, wires, skin preparation pads, notebook with pen, trimmer (optional for those with hairy thighs), and extra AA batteries. If you need additional supplies at any time, call the research assistant.

Before beginning the treatment, you must protect your skin.

Skin Preparation:

1. Always check the skin carefully prior to beginning stimulation. The skin should not have any cuts, open sores, rashes, or inflammation.

[figure not shown]
What to do if a skin problem occurs: Carefully wash and dry the area with mild soap (unscented), rinse, and use a soft towel to dry the area. Call the research assistant and inform them of your skin problem. You will need to pause treatment until your skin heals.

2. If your skin is healthy, wash the skin where the patches will be placed (see picture below). Do not apply any lotions, gels, or perfumes to the skin. Gently dry the skin with a soft towel.
3. If there is any hair in the area where the patches will be placed, remove the hair with a trimmer. **Do Not** use a razor as this will lead to skin irritation and minor cuts.
4. After washing, drying, and the removal of hair, open the skin preparation pads (SKIN-PREP) found in the canvas bag and thoroughly wipe the area where the patches will be placed. Wait 30 seconds for the SKIN-PREP to dry, then place the patches.

Using Your Empi Unit

1. Make sure that the skin where the patches will be placed has been washed, dried, and SKIN-PREP applied.
2. Make sure that the unit is turned off.
3. Open the sealed bag with the patches found in the canvas bag. Gently peal the patches off the plastic sheet and save the sheet to return the patches when your session is complete. The patches are reusable and should be changed every week. If the patches don't want to stick they maybe dry. You can add 1 or 2 drops of water to the patch, if it still doesn't stick, use a new set.
4. Plug the wire connector from the patch to the wire on the machine. Note: The wire connectors may connect to either the red or black connectors. The black wire connected to the patch at the top of the thigh and the red connector the patch near the knee. If there is wire damage call research assistant for a new set.
5. Place the patches in the correct locations as indicated in the diagram on page 2. Stick the center of the patch on the desired area of the skin, and then flatten the sides of the patches onto the skin.

6. Remove the unit from the canvas bag and turn the unit on using the ON/OFF button in the middle of the bottom row on the unit, just below the screen. When you turn on the unit, the screen will present the Empi logo (See picture above).
7. Next, the screen should display an “In-Progress” message indicating that the unit is ready for use.
 - a. If the screen goes to a menu that displays options for you to select (i.e., NMES, TENS, EDMEA, CONFIG), call the research assistant as additional directions will be needed for you to safely use the machine.
8. Once the “In-Progress” screen appears, you need to increase the level of intensity for treatment. Adjust the intensity to the level specified by the research assistant.
 - a. To increase the intensity for Channel 1, press the top button on the left-hand side of the screen. To decrease the intensity for Channel 1, press the bottom button on the left-hand side of the screen.
 - b. To increase the intensity for Channel 2, press the top button on the right-hand side of the screen. To decrease the intensity for Channel 2, press the bottom button on the right-hand side of the screen.

- c. Note: Once the intensity is set and left alone for 20 seconds, the unit will lock the buttons to prevent an unwanted change. In order to change the intensity after the unit is locked, press the decrease intensity button on the desired channel to unlock the unit so you can change the intensity.
- d. Unit will stop running after 15 minutes. You can now turn off the machine by pressing of on/off button for 2 sections and remove the patches.

9. Removing the patches

- a. Turn off the unit before removing the patches.
- b. Carefully pull the patch off the skin starting at a corner. The wire connectors should **not** be used to help pull the patches off! Pressing on the skin with your other hand close to where you are removing the patch makes removal easier.
- c. Reapply the patches to the liner. Making sure the patch is flat on the liner.
- d. Separate the wire from the connector of each patch by gently unscrewing and lightly tugging where they join. Seal the bag with the patches to keep them from drying out. Return the machine and patches to the canvas bag for storage until your next use.

10. Carefully wash and dry the skin where the patches were applied with mild soap, rinse, and wipe with a soft towel. Some redness is expected after immediate removal of patches. If the redness remains after an hour or is bothersome in any way, write down what you are seeing and feeling in the notebook included in the canvas bag and call the research assistant. (For details see Skin Prep section on page 2)

Caring for the Empi Unit:

Maintenance:

- The unit is designed to function without regular maintenance. Call the research assistant if you have concerns.

Cleaning:

- If the unit becomes dirty, use a nonabrasive, damp cloth to wipe off the unit. Refrain from use any chemicals or cleaning solutions to clean the unit. Do not place the unit in any liquids.

Storage:

- Although the unit will be used regularly, avoid leaving the unit out following use. The wires are easily tangled, targets for pets, or a potential tripping hazard. Use the canvas bag provided to store the unit at room temperature.

Having problems with the Empi Unit?

If the unit displays the low battery symbol or message or the unit will not turn on replace the batteries.

How to replace the batteries:

1. Turn off the device.
2. Turn the unit over so the backside towards you. Remove the battery cover by placing your thumb on the notch and the bottom backside of the unit and pushing up while pulling out.
3. Remove the old batteries.
4. Place new batteries in the unit by matching the + and – ends of the battery with those on the unit. Only use the AA batteries provided by the study to replace the batteries in the unit. If you do not have any AA batteries left, call the research assistant.
5. Replace the battery cover by inserting the small lip at the base of the cover. Then, insert the top of the cover and press until it clicks securely in place. Check the batteries in the unit and make sure that the + and – ends on the batteries match the + and – symbols on the unit. Check to ensure that there is nothing hindering the batteries from touching the respective + and – ends of the unit.

If the unit powers on but the buttons are not functioning properly, check the following:

- a. Disconnect the wires from Channel 1 and Channel 2.
- b. Remove the batteries from the unit. And leave the batteries out for 10 seconds.
- c. Replace the batteries in the unit and try running the treatment again.

If the unit powers on and the screen appears correct but you do not feel any stimulation, check the following:

- a. Check to make sure that the intensity is to the minimum level specified by study personnel.
- b. Check the lead wires and make sure that they are properly connected to both the patches and the unit in the proper locations (i.e., Channel 1 and Channel 2).
- c. Check the wires for any damage or disconnections to either the unit or the patches. If the wires are damaged on the machine call the research assistant for a new pair. If the connection on the patches is damaged, use a new pair.

If the unit powers on and the screen displays an “OPEN” error message check the following:

- a. Turn off the machine and check to make sure that the patches and wires are connected correctly to one another and the unit. If they are, remove the patches from your skin check “stickiness” of the patches and add 1-2 drops of water if needed. Then, reapply the patches to the skin. If there still isn’t a good response from the machine, or the patches were very “sticky” replace the patches with a new set.
- b. If the error message still appears when you turn on the machine, then call the research assistant and report the problem.

If the unit powers on but the intensity cannot be changed, try unlocking the device (page 5 section #8).

If the unit is damaged or if it is not working correctly call the research assistant. Do not attempt to repair or use the unit.

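### The set-up procedure for the sham (TENS) unit ends by locking NMES and hiding TENS

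*Combined protocol and SAP*

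**What the plan says.** **Sham definition.** Section 5 (Intervention and Sham/Wait List Control Conditions) places sham electrodes at the same sites as active ones, sets the machine to TENS rather than NMES, and limits intensity to tingling.

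**Sham set-up.** Section 12B has a procedure headed "EMPI Standard Operating Procedure for setting up TENS". It selects TENS and programs 15 minutes, 100 Hz, a 15 s cycle, 50% span and the MOD mode. It also warns that "you may not need to make adjustments to the machine due to previous programming". On intensity, the RA is told of participants: "They should not increase the intensity to the point where a muscle contraction happens". Three lock steps follow. The RA opens the lock menu, locks NMES large muscles, and hides small muscles so that participants no longer see that option. The last instruction is: "Repeat for TENS and Edema then press home and note only L. Muscles is an option besides config".

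**Active set-up.** The NMES procedure in the same section ends with the same three lock steps. Its coaching is the opposite: "The intensity needs to be strong enough to cause the muscle to contract".

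**Return of units.** Step 3 has staff "identify if NMES or TENS showing on the main menu" and enter the result in REDCap. Step 10 clears the usage data and concludes: "The data has been erased from the machine and is ready for the next participants set up".

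**Participant handout.** After power-on the participant should see an in-progress "message indicating that the unit is ready for use". A participant who sees a menu of modes instead must call the RA.

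**The concern.** The randomised contrast is NMES against TENS, and these lock steps decide which mode a participant takes home. In the sham procedure they keep the active mode and remove the sham mode. The closing check makes this worse, because it tells an RA who has followed every step that the unit is correct when it is not.

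If such a unit runs the large-muscle programme, the sham participant receives the active-arm mode with parameters the sham procedure never set. They could be defaults or a previous participant's settings: the procedure allows for earlier programming, and the return procedure mentions clearing usage data but not settings. If the unit runs no usable programme, sham delivery fails. Neither outcome is the protocol's sham. Active stimulation in the sham arm would bias the group contrast toward the null, and no planned analysis corrects for it.

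**Working it through.** The main check is a comparison of texts.

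**1. End state of each unit, following the written steps**

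| Menu option | Sham required by Section 5 | TENS procedure as written | NMES procedure as written |
|---|---|---|---|
| NMES large muscles | hidden | locked, visible | locked, visible |
| NMES small muscles | hidden | hidden | hidden |
| TENS | locked, visible | hidden | hidden |
| Edema | hidden | hidden | hidden |

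The first column is what the sham definition implies for the lock menu. The second and third columns are identical. On the two rows that separate the arms, the sham procedure gives the reverse of what is needed.

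**2. Is this an artefact of text extraction?** No. The lock steps come directly after coaching that applies only to sham (stay below contraction) and before the heading of the NMES procedure. They belong to the TENS procedure.

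**3. Do the documents agree elsewhere?** No. Return step 3 expects some units to show TENS on the main menu. A sham unit locked as written would not.

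**4. Would a written safeguard catch it before or during treatment?**
- The closing check of the sham procedure names the wrong mode.
- Comfort testing comes before locking, so it cannot verify the locked state. Section 5 requires a return demonstration but does not place it after locking.
- The weekly calls cover protocol and placement, tolerance, skin and machine problems. Mode is not listed.
- The oscilloscope check compares displayed with actual current output.
- The handout prompts a call only if a menu appears.
- The return entry would correctly read NMES, but only after that participant's treatment, and no step compares it with allocation.

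**5. Exposure before the return check.** Inputs: 5 sessions a week, 6 weeks and 15 minutes a session (Section 5, NMES Protocol Summary); 27 completers per group (Section 8, Power Considerations).
- Sessions per sham participant: 5 × 6 = 30.
- Time per sham participant: 30 × 15 min = 450 min = 7.5 h.
- Ceiling over the sham arm: 27 × 30 = 810 sessions.

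These figures are the planned dose. They assume full adherence and no earlier detection, and the last also assumes that every sham unit is mis-set. They say nothing about how likely the error is or how large its effect would be.

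**6. A separate, minor point on the active dose.** The NMES Protocol Summary gives 15 stimulations per 15-minute session. The programmed cycle is 2 + 11 + 2 = 15 s on plus 15 s off, or 30 s, with both legs together. That gives 900 / 30 = 30 stimulations. Fifteen would take 15 × 30 s = 450 s = 7.5 min. This has no bearing on the severity of the sham problem.

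**The case against.** The strongest reply is that the harm needs a chain of events the documents do not establish. The RA must follow the steps literally after having just programmed TENS, the locked unit must start in the large-muscle programme, and nobody must notice. The device manual is not among the documents, so the second link is unknown. The RA is trained in both set-ups and might well see that hiding the mode just programmed makes no sense. The intended sham is never in doubt: the protocol text, the heading, the programming steps and the return procedure all point to TENS, so this looks like a copying slip. If power-on shows a menu, the participant calls and the fault surfaces at first home use. A weekly call might pick up unexpected contractions, and machines are calibrated before each participant. Sham participants are also coached to stay below contraction, so part of the contrast could survive.

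Most of this stands as a limit on what can be said to have happened. It does not repair the procedure. None of these safeguards is a documented mode check before issue, and calibration is not described as one. The coaching is given before locking, and nothing shows that an intensity chosen on TENS stays below contraction on the large-muscle programme. A procedure that is right only when staff depart from it does not control which treatment is delivered.

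**Conclusion.** The concern holds, and the procedure must be fixed. As written, it produces a sham unit that does not meet the protocol's own definition of sham, and its closing check confirms the wrong mode. Confidence in this is high because it rests on the text alone.

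The consequence is less certain. Bias toward the null requires that the steps were followed literally and that the locked unit then ran the large-muscle programme. The documents settle neither, so the bias cannot be computed. What can be bounded is exposure before the return check: up to 30 sessions per affected sham participant, and at most 810 over 27 completers.

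**What to change.** 1. In the TENS procedure, rewrite lock steps 2 and 3 so that TENS is locked and visible, and large muscles, small muscles and Edema are hidden. The closing check should confirm that TENS is the only option besides config. Try the new sequence on a unit before adopting it.
2. Before hand-over, have the RA record the visible mode against allocation. The RA already holds the allocation file, so the entry can be kept with it and the PI stays blinded.
3. Have the RA check units already issued and compare past return-mode entries with allocation. A sham participant whose unit read NMES at return would identify an affected case.
4. Separately, correct the NMES Protocol Summary to about 30 stimulations per session, or shorten the session if 15 was intended.

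The cost of items 1 and 2 is two rewritten steps, one corrected check and a few seconds' entry per unit. Item 3 is a one-off comparison of records already held, plus a check of units now in use. Design, sample size and analysis are unchanged.

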gentle pumping sensation is felt. Participants will direct the amount of stimulation acceptable on both thighs to improve acceptance of the modality.^{10,24,29-31} To assist better tolerance large electrodes (2x4) will be used and participants will also be instructed to be in a seated position with chair close to the wall so that their leg is 90-degree angle and then push against the wall to decrease any uncomfortable feeling during the contraction. For the Sham group, electrodes will follow the same landmarks, but the stimulation will only increase to an intermittent tingling sensation with the machine setting on TENS instead of NMES which is not enough to make noticeable changes in muscle mass or circulation.³² Participants in both groups will be given written instructions and contact information of the person (RA) to contact should there be any problems or concerns with the intervention. All participants will do a return demonstration to assure proper knowledge has been gained. Adherence to the study protocol will be determined by the amount of time the EMPI machine records that it was used, the intensities utilized along with verbal verification during the weekly phone calls.

NMES Protocol Summary

- 5 sessions per week for 6 weeks done independently at home, with 15 minutes per session (15 stimulations per day/session, 15 seconds stimulation on, 15 seconds recovery time) to both legs.
- Intervention group only: We expect the participant to develop tolerance to the treatment and thus increase the intensity of the NMES over time.
- At the end of the trial, the participants will return to have all measures repeated. Sham group will then be offered the active treatment. In previous HF studies (non-NMES) done by the mentor of this grant, no participants have accepted the offer of the intervention after completion of the sham/control so this number is expected to be very small.
- Participants will be encouraged to begin a formalized exercise plan such as Silver Sneakers, a home based cardiac rehabilitation or institutional cardiac rehabilitation program.
- Finally, 3 months after the intervention/sham was completed participants will return one final time to have all measures repeated to allow for evaluation of activity levels following completion of the intervention.

Retention

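### The lock steps that close the sham (TENS) set-up SOP are the NMES ones: followed literally, they hide TENS and leave NMES Large Muscles as the only option shown on a sham unit

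*Combined protocol and SAP*

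**What the plan says.** Section 5 (Intervention and Sham/Wait List Control Conditions) uses the same electrode sites in both arms and runs sham at a tingling level only, "with the machine setting on TENS instead of NMES which is not enough to make noticeable changes in muscle mass or circulation".

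The Section 12B SOP for setting up TENS starts in line with that. Step 3 is "Press the TENS button (bottom Left", and steps 4 to 9 set a custom TENS program. On intensity, the RA is told: "They should not increase the intensity to the point where a muscle contraction happens".

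The SOP then has the RA lock the unit in three steps. Step 2 reads: "Notice the NMES L. Muscles and press the right top button, which locks that option". Step 3 hides the small-muscle option with two presses and ends: "Repeat for TENS and Edema then press home and note only L. Muscles is an option besides config". The same three steps close the SOP for setting up NMES.

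The Section 12B SOP for returned units, step 3, has staff turn the unit on, "identify if NMES or TENS showing on the main menu and enter that data into RedCap".

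**The concern.** Sham is the only comparator for all four aims, and this SOP is the only written set-up instruction for the sham device. Its last action hides the program it has just set, keeps the active arm's program on display, and asks the RA to confirm that state as correct. An RA who checks the work against the SOP is told that a mis-locked sham unit is right.

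If a sham unit then ran Large Muscles at home, that participant would get some of the active treatment and the group difference would shrink. The bias would run toward no difference; it could not create a false benefit. If the RA instead improvised a working sham lock, the actual procedure would be undocumented and could differ from one RA to another.

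**Working it through.** The point depends on no figure in Section 8, so the check compares texts.

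**1. The two lock blocks.** Compared as text, the three lock steps in the TENS SOP and the three in the NMES SOP are identical. They fit the NMES SOP. No other part of the document gives a lock sequence for sham units.

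**2. What the steps do to a sham unit.** By the SOP's own account, one press locks an option and two presses remove it from the participant's view.

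| Option | State after the written steps | State a sham unit needs |
|---|---|---|
| NMES Large Muscles | locked, shown | hidden |
| NMES Small Muscles | hidden | hidden |
| TENS | hidden | locked, shown |
| Edema | hidden | hidden |

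Two of the four options end in the wrong state, and they are the two that define the arms.

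**3. Consistency with the return SOP.** Return step 3 makes sense only if some units show TENS. Under the TENS SOP as written, the main menu of a sham unit would not. The two SOPs cannot both be followed as intended.

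**4. What would happen at home.** The documents do not say which program a locked unit opens to. Three outcomes fit the text:
- (a) It opens in Large Muscles. The participant receives NMES, at settings that are not known. The TENS SOP never programs Large Muscles. Both set-up SOPs say "you may not need to make adjustments to the machine due to previous programming", and the return SOP clears usage data but mentions no reset of programs. Active-arm settings could therefore remain on a reused unit, but this is not established.
- (b) It opens on a menu. The patient instructions (Using Your Empi Unit, step 7a) cover this case: "If the screen goes to a menu that displays options for you to select", the participant calls the RA. No written correction follows.
- (c) The TENS program already set keeps running, and sham is unaffected.

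**5. What the return entry can show.** An NMES entry against a sham allocation would flag a mis-locked unit, but only at the end of the 6 weeks. It would not separate (a) from (c). In case (c) even the reading is uncertain: step 3 is read at power-on, before Home is pressed in step 4, and the patient instructions say a unit normally powers on to an in-progress screen.

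**6. Scope and size.** The SOP governs every sham unit: at least 27 planned completers, up to 5 × 6 = 30 sessions each. That counts who is covered by the instruction, not who was exposed. If q is the share of sham units that ran NMES and g the share of the NMES benefit obtained at an intensity chosen for tingling, the group difference retained is 1 − q·g. Both q and g are assumptions that can lie anywhere from 0 to 1, so the retained fraction runs from 1 (no effect) to 0. Nothing in the documents narrows this.

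**The case against.** The strongest reply is that this is a copying slip in an appendix and the intent is plain. Section 5, the TENS programming and the return SOP all agree that sham runs on TENS. An RA trained in both set-ups, who has just programmed TENS, would probably notice being told to hide it. Every participant gives a return demonstration, and weekly calls ask about protocol and tolerance. The patient instructions (step 8) tell participants to use the intensity the RA specified, which for sham is below contraction. All of this stands, and it limits how likely and how large any harm is.

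It does not remove the error. The SOP's own confirmation step endorses the wrong state. The comfort test comes before locking, and no written step restarts the unit afterwards. The oscilloscope check in Section 5 concerns current output, not the program.

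A reader might infer that the sham arm received active treatment. The documents do not show this: hiding an option from the menu is not shown to replace a program already set, and the Large Muscles settings on a sham unit are unknown. A reader might also infer that the return field is useless and that a null result could never be told apart from a sham failure. That goes too far, because NMES recorded for a sham participant is itself the warning sign once compared with allocation. Nor can a loss of power be quoted as the size of the problem, because any such figure would come entirely from assumed q and g.

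**Conclusion.** Wrong as written, moderate severity. That lock steps 2 and 3 contradict Section 5, the TENS programming and the return SOP follows from the text with no assumption. Any effect on participants assumes two things: that an RA followed the steps literally, and that the locked device behaved as in outcome (a) or (b). Exposure of sham participants to NMES is possible but not shown. The dilution is unknown and may be zero; if present, it acts against finding a benefit. The sample size, the stated power and the analysis model are not in question.

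**What to change.** In the SOP for setting up TENS, replace lock steps 2 and 3 with: lock TENS; hide Large Muscles, Small Muscles and Edema; press Home and confirm that TENS is the only option besides config. By the SOP's own convention that is one press for TENS and two for each of the others; try the sequence on a unit before issuing the text.

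In both set-up SOPs, add a step after locking: turn the unit off and on, and confirm that it opens in the assigned program. Have the RA enter that program in REDCap at dispatch, in a field hidden from the blinded data collector, and compare it with the allocation and the return entry.

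Check the lock state of sham units already issued, and review the return entries for those already back. Analyse as randomized, and report any sham unit that ran NMES as a protocol deviation.

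The cost is two corrected SOP lines, about a minute of RA time per unit and one form entry. NMES dosing, the participant handout, sample size and analysis do not change.
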